### **5.4 Decision to Administer Second Vaccination**

Prior to administering the second vaccination, subjects will have the following procedures/assessments performed:

- Inclusion/exclusion criteria recheck (including absence of acute illness or new medical condition)
- Oral temperature
- Targeted physical examination
- Vital signs
- Review of clinical safety laboratory test results to date
- Urine pregnancy test, as applicable
- Nasopharyngeal swab on Day 15 to check for SARS-CoV-2 infection (result must be received by the CRU and negative prior to the second vaccine administration).
- Medical history since last visit including AE assessment for SAEs, Grade 3 AEs or AESIs that are possibly, probably, or definitely related to study vaccine without a plausible alternative explanation
- Check of Study Halting Rules ([Section 5.7.2](#))

All assessments must be normal or be in agreement with inclusion/exclusion criteria in order for a subject to receive the second vaccination dose.

For all of the sentinel groups, the iSRC will meet to review the sentinel subjects' safety and tolerability data through Day 8. In the event that iSRC has not met for the post Day 8 review because the entire sentinel group (n = 3) has not completed Day 8 before a sentinel subject is to receive the second vaccine on Day 22, the iSRC will meet on an ad hoc basis, to ensure there are no safety concerns and that none of the Individual Discontinuation Criteria ([Section 5.5](#)) or Study Halting Rules ([Section 5.7.2](#)) have been met, prior to the sentinel subjects receiving the second vaccine.

## **5.5 Individual Discontinuation Criteria**

The occurrence of the following findings in an individual subject may result in discontinuation from the study vaccine. Subjects will be asked to participate in the scheduled Follow-up Visits, including at a minimum Day 365, to check safety and immunogenicity.

- Subjects experiences an SAE assessed as possibly related, probably related, or related to study vaccine without a plausible alternative explanation.
- Subject has generalized urticaria during the 7-day post vaccination period.
- Subject develops a Grade 4 local reaction for which there is no alternative plausible explanation.
- Subject experiences laryngospasm, bronchospasm, or anaphylaxis after vaccine administration considered related to the vaccine.
- Subject develops a fever  $>40^{\circ}\text{C}/104^{\circ}\text{F}$  during the 7 days post vaccination period that is assessed as possibly related, probably related, or related to study vaccine without a plausible alternative explanation.
- Single Grade 3 AEs or AESIs that are possibly, probably, or definitely related to study vaccine without a plausible alternative explanation.
- Subject experiences any Grade 3 or higher abnormality in the same laboratory parameter determined by the Investigator or medical monitor as clinically significant and that are assessed as possibly related, probably related, or related to study vaccine without a plausible alternative explanation.

## **5.6 Subject Withdrawal**

Subjects are free to withdraw from the study at any time, for any reason, and without prejudice to further treatment. The Investigator may withdraw a subject if, in the Investigator's judgment, continued participation would pose unacceptable risk to the subject or to the integrity of the study data. All procedures for early withdrawal must be completed. Reasons for withdrawal may include:

- AE
- SAE that is possibly related, probably related, or related, without a plausible alternative explanation
- Lost to follow-up
- Physician decision
- Pregnancy
- Protocol deviation
- Study terminated by Sponsor
- Withdrawal by subject
- Death
- Other

Subjects who are withdrawn for reasons other than AEs may be replaced.

In the event of a subject's withdrawal from study vaccine, the Investigator will promptly notify the Sponsor and will make every effort to complete the EOS assessments, unless the subject withdraws consent. All withdrawn subjects with ongoing clinically significant clinical or laboratory findings will be followed until the finding is resolved or medically stable; reasonable attempts will be made to follow-up with subjects. The subject will also be asked to participate in a Follow-up Visit at approximately Day 365 to check safety and immunogenicity.

Subjects may be withdrawn from receiving the second dose of the study vaccine if they meet specific Study Halting Rules (see [Section 5.7.2](#)) or Individual Discontinuation Criteria ([Section 5.5](#)). If a subject is withdrawn due to meeting a Study Halting Rule or Individual Discontinuation Criteria, they will be asked to participate in the scheduled Follow-up Visits, including at a minimum Day 365, to check safety and immunogenicity.

## **5.7      Independent Safety Review Committee, Study Stopping Rules, and Study Termination**

### **5.7.1      Independent Safety Review Committee**

A safety review will be performed by the iSRC according to details established at the start of the study and provided in the iSRC charter. The Investigator will provide a brief summary to the iSRC of any pertinent safety events prior to the iSRC meeting. The three member iSRC will consist of, at a minimum, two physicians with experience in vaccines and one statistician.

The iSRC will review the safety and tolerability data through Day 8 for each of the sentinel subject groups prior to the enrollment of the remaining cohort subjects. In the event that iSRC has not met for the post Day 8 review because the entire sentinel group (n = 3) has not completed Day 8 before a sentinel subject is to receive the second vaccine on Day 22, the iSRC will meet on an ad hoc basis, to ensure there are no safety concerns and that none of the Individual Discontinuation Criteria ([Section 5.5](#)) or Study Halting Rules ([Section 5.7.2](#)) have been met, prior to the sentinel subjects receiving the second vaccine.

The iSRC will be convened to review all available safety data including solicited AEs, unsolicited AEs, SAEs, MAAEs, NOCDs, AESIs, vitals, safety laboratory, and physical exams results of Part A low dose when all subjects have received the first vaccination and have all safety data through Day 8. If there are no safety concerns after the iSRC meeting, study enrollment will continue to Part A high dose and Part B low dose. The same strategy will be used to move from Part B low dose to Part B high dose.

The iSRC will also meet when a minimum of 23 subjects have completed Day 29 after the second vaccination for Part A (high and low dose) and for Part B (high and low dose) to review safety data to ensure that there are no concerns.

The iSRC will be asked to review unblinded immunogenicity and safety data when the first 30 subjects vaccinated in the Part A low dose group (including active and placebo subjects) have data available from Day 1 through Day 43 for an assessment of the risk-benefit of the trial. For the

CONFIDENTIAL

interim analysis, treatment codes will only be unblinded by treatment group (not by individual subjects) and only after the data are deemed ready for the analysis and the data has been monitored. The unblinded review will be completed by the iSRC only and the other team members (CRO [except for the unblinded team members preparing the data for unblinded iSRC review], Investigator, and site personnel) will remain blinded. The Sponsor will be unblinded at the interim analysis (Day 43). The iSRC/Sponsor will communicate immunogenicity data to the study team in a blinded manner so that clinical development decisions for additional studies can be made by the Sponsor.

Cohort dose continuation/escalation will only occur if the iSRC determines that the current dose was safe and well tolerated. If justified by cumulative safety and tolerability data, the iSRC can dose escalate per protocol, select an intermediate dose (lower or higher), or repeat a dose. The decision to allow dose continuation/escalation into the next cohort will be documented and this decision, along with the safety information, will be communicated to the site.

The iSRC will also meet on an ad hoc basis if any of the Study Halting Rules are met (Section 5.7.2). If a Study Halting Rule is met, the iSRC will proceed with an unblinded review of available safety data. After the meeting, the iSRC will make 1 or more of the following recommendations:

- All vaccinations should resume
- Specific treatment groups should be discontinued while other treatment groups should resume vaccinations
- No vaccinations should resume
- Modifications to study conduct (eg, additional safety or laboratory assessments)

The blinded medical monitor will also assess cumulative safety information for this study per the Medical Monitoring Plan and advise the Sponsor of any of the safety findings (Section 5.7.2) have occurred.

The iSRC will review unblinded safety data for any subject who dies, requires ICU admission due to SARS-CoV-2 infection, develops an AESI ([Section 8.2.2](#)) of autoimmune disease or potential immune-mediated medical condition ([Appendix B](#)), or experiences vaccine-associated enhanced respiratory disease. If the subject had received TAP-COVID-19, the iSRC may decide whether a study halt for vaccine-enhanced disease is required based on a review of all available clinical and preclinical safety and immunogenicity data.

## **5.7.2                    Study Halting Rules**

The occurrence and confirmation of 1 or more of the following findings will result in suspension of further enrollment and study vaccine administration pending urgent review (within 1 week) of the safety data by the iSRC. Subjects who are withdrawn from study vaccine (if applicable) will continue to be monitored ([Section 5.6](#)) for safety and immunogenicity.

1. One or more subjects experience an SAE assessed as possibly related, probably related, or related to study vaccine without a plausible alternative explanation.

CONFIDENTIAL

2. One or more subjects have generalized urticaria during the 7-day post vaccination period.
3. One or more subjects develop a Grade 4 local reaction for which there is no alternative plausible explanation.
4. One or more subjects experiences laryngospasm, bronchospasm, or anaphylaxis after vaccine administration considered related to the vaccine.
5. One or more subjects develop a fever  $>40^{\circ}\text{C}/104^{\circ}\text{F}$  during the 7 days post vaccination period that is assessed as possibly related, probably related, or related to study vaccine without a plausible alternative explanation.
6. Two or more subjects within an individual treatment group, or 2 or more subjects across treatment groups, experience any Grade 3 or higher abnormality in the same laboratory parameter determined by the Investigator or medical monitor as clinically significant and that are assessed as possibly related, probably related, or related to study vaccine without a plausible alternative explanation.

Note: An unblinded statistician or designee will assist with determining whether stopping rule #6 is met.

7. Two or more subjects across treatment groups experience a Grade 3 or higher AE, MAAE, or AESI of the same or similar preferred terms (as categorized by MedDRA) assessed as possibly related, probably related, or related to study vaccine without a plausible alternative explanation.
8. Any subject with severe SARS-CoV-2 infection will be assessed for the possibility of vaccine-associated enhanced respiratory disease. Severe SARS-CoV-2 infection is defined as individuals who have virologically confirmed SARS-CoV-2 infection with any of the following:
  - Clinical signs at rest indicative of severe systemic illness (respiratory rate  $\geq 30$  breaths per minute, heart rate  $\geq 125$  bpm,  $\text{SpO}_2 \leq 93\%$  on room air at sea level or  $\text{PaO}_2/\text{FiO}_2 < 300$  mmHg)
  - Respiratory failure (defined as needing high-flow oxygen, noninvasive ventilation, mechanical ventilation or ECMO)
  - Evidence of shock (systolic blood pressure  $< 90$  mmHg, diastolic blood pressure  $< 60$  mmHg, or requiring vasopressors)
  - Significant acute renal, hepatic, or neurologic dysfunction
  - Admission to an ICU
  - Death due to SARS-CoV-2 infection

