

on Day 1 and Day 22 (<math>\pm 3</math> days)
 
Treatment B: TAP-COVID-19 vaccine (45 <math>\mu</math>g) + CpG (0.5 mg) IM injection on Day 1 and Day 22 (<math>\pm 3</math> days)
 
Treatment C: Placebo (buffered saline solution) IM injection on Day 1 and Day 2 (<math>\pm 3</math> days)
 
Study vaccine will be prepared by an unblinded site pharmacist and administered at the clinical research site on Day 1 and Day 22 (<math>\pm 3</math> days) by unblinded clinical research unit (CRU) personnel. Subjects will be observed for immediate AEs and/or reactogenicity for approximately 60 minutes after administration of vaccine. Subjects will be provided with a Diary Card and will be trained to record specifically elicited systemic and local symptoms daily as well as any additional AEs during the 7-day follow-up period after each vaccination. Visits will be conducted at the clinical site on an outpatient basis or as a telephone visit per the Schedule of Assessments and Procedures. Subjects will participate in the study for approximately 1 year from the first dose.
 
AEs and concomitant medications will be captured through Day 43. Blood and serum samples for safety laboratory tests, RBD IgG and IgM antibodies and neutralizing antibody titers, cell-mediated immunity, and other future biomedical research will be obtained at baseline and before administration of vaccine dose 2 and after each vaccination per the Schedule of Assessments and Procedures. SAEs, MAAEs, NOCDs, and AESIs only will be captured after Day 43 to study completion (Day 365 [approximately 1 year after first vaccination]).
 
Prior to receiving a second dose of vaccine, subjects will have the following assessments performed to ensure eligibility: vital signs (including temperature), review of clinical laboratory test results to date, nasopharyngeal swab Day 15 to check for SARS-CoV-2 infection (reverse transcription polymerase chain reaction [RT-PCR] result must be received by the CRU and negative prior to the second vaccine administration), medical history since last visit including AE assessment for SAEs, Grade 3 AEs, or AESIs that are possibly, probably, or definitely related to study vaccine without a plausible alternative explanation, targeted physical examination, recheck of eligibility criteria, and pregnancy test (as applicable).
 
Subjects will be monitored for SARS-CoV-2 exposure for potential asymptomatic infection throughout the study.
 

• If a subject has a positive or borderline ELISA anti-N IgG result, sites should have the subject return for an unscheduled PCR. If the ELISA is positive and the PCR is negative, the sites should follow the subjects using the standard of care under Investigator discretion, retesting ELISA at the next study visit(s) or sooner (per the Investigator's decision).

• If the subject has a positive or borderline ELISA anti-N IgG AND a positive PCR test, the clinical sites should bring the subjects back for repeat PCR testing as described below.

• The clinical sites should continue to collect PCR tests if a subject is experiencing possible COVID-19 symptoms, or had possible exposure to SARS-CoV-2 (ie, close contact tests positive for SARS-CoV-2). Testing will occur every 2 weeks for a total of 4 weeks (if 2 consecutive negative tests) or until negative (x2) after a positive result. Positive results will be reported as an AESI and subjects followed for disease severity, duration, and outcome.

 
Subjects who are seropositive for SARS-CoV-2 and asymptomatic will be allowed to enroll into Parts A and B of the study as long as the subject is RT-PCR negative.
 
Interim Safety Data Reviews:
 
For all of the sentinel groups, the iSRC will meet to review the sentinel subjects' safety and tolerability data through Day 8. In the event that iSRC has not met for the post Day 8 review because the entire sentinel group (<math>n = 3</math>) has not completed Day 8 before a sentinel subject

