### **8.2.4       Relationship to Study Vaccine**

The relationship of an AE to the study vaccine should be determined by the Investigator according to the following criteria:

- Not related: The event is most likely produced by other factors such as the subject's clinical condition, intercurrent illness, or concomitant drugs, and does not follow a known response pattern to the study vaccine, or the temporal relationship of the event to study vaccine administration makes a causal relationship unlikely

- Related: The event follows a reasonable temporal sequence from the time of drug administration, and/or follows a known response pattern to the study vaccine, and cannot be reasonably explained by other factors such as the subject's clinical condition, intercurrent illness, or concomitant drugs

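### Does halting rule 7 leave out two related Grade 3 events in the same treatment group, and do the mixed causality terms change what halts the study?

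*Combined protocol and SAP*

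**What the plan says.** Section 5.7.2 lists eight findings that suspend enrollment and vaccination until the safety review committee (iSRC) has met.

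- **Rule 6 (laboratory).** It counts "Two or more subjects within an individual treatment group, or 2 or more subjects across treatment groups, experience any Grade 3 or higher abnormality", provided both fall on one laboratory parameter. A note adds: "An unblinded statistician or designee will assist with determining whether stopping rule #6 is met".
- **Rule 7 (clinical events).** It counts "Two or more subjects across treatment groups experience a Grade 3 or higher AE, MAAE, or AESI of the same or similar preferred terms", with a relatedness condition. There is no within-group limb and no note. The synopsis repeats the wording of both rules, so it does not settle the point.
- **Who applies the rules.** Section 5.7.1 says the committee works "according to details established at the start of the study and provided in the iSRC charter". It also says "The blinded medical monitor will also assess cumulative safety information for this study per the Medical Monitoring Plan" and advises the sponsor if a Section 5.7.2 finding has occurred.
- **Causality terms.** Rule 1 reads "One or more subjects experience an SAE assessed as possibly related, probably related, or related to study vaccine without a plausible alternative explanation"; rules 5, 6 and 7 and Section 5.6 use the same three terms. The second-dose text in the synopsis and Sections 4.1 and 5.4 refers to "AESIs that are possibly, probably, or definitely related to study vaccine without a plausible alternative explanation". Section 5.5 uses both forms. The scale in Section 8.2.4, to which Section 8.1 points for recording, has only two levels, and its upper level requires that the event follow a plausible time course or known pattern "and cannot be reasonably explained by other factors".

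**The concern.** Two adjacent rules with different counting language invite the inference that the difference is deliberate. If rule 6 needed its within-group limb, then rule 7, which lacks it, might require the two subjects to come from different groups. Two vaccine recipients in one arm with the same related Grade 3 event would then not trigger a mandatory suspension, while one vaccine and one placebo recipient would. In a first-in-human study that would be an odd blind spot. It would be widest in the first cohort, which has a single vaccine arm plus placebo.

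The causality wording raises a second doubt. Investigators record one of two levels, while the rules speak of three, in two different forms, and no section maps one set onto the other. Someone applying the rules could ask which recorded category satisfies them.

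**Working it through.** **1. Counting in rule 7: the passages side by side.**

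- A test that requires different groups can be applied only by someone who knows each subject's group. A pooled count needs no treatment codes.
- Section 5.7.1 gives cumulative review against Section 5.7.2 to a blinded monitor.
- Section 5.7.2 assigns unblinded help to rule 6, the rule with a within-group limb, and to no other.
- Both facts fit a rule 7 count over all groups together, so that any two subjects qualify. On that reading the within-group limb of rule 6 is surplus, and rule 7 has no gap.

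**2. What the other reading would do.** The protocol gives no operating characteristics for the halting rules and no event rates, so there is no stated figure to reproduce. Section 9.3 gives 30 vaccine and 15 placebo subjects per cohort; 4 × (30 + 15) = 180 agrees with Section 9.1. All event rates below are assumed. Rule 7 is taken alone, with independent subjects.

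- Pooled: P = 1 − P(0 events) − P(exactly 1 event).
- Different groups, one cohort: P = [1 − (1 − q)^30] × [1 − (1 − b)^15], with q the vaccine rate and b the placebo rate.

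For q = 0.05 and b = 0.01:

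- (1 − q)^30 = 0.2146 and (1 − b)^15 = 0.8601, so P(0) = 0.1846.
- P(1) = 30 × 0.05 × 0.95^29 × 0.8601 + 0.2146 × 15 × 0.01 × 0.99^14 = 0.3194.
- Pooled: 1 − 0.1846 − 0.3194 = 0.4960.
- Different groups: 0.7854 × 0.1399 = 0.1099.

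| Setting | Low-dose / high-dose / placebo rate | Pooled | Different groups | Gap |
|---|---|---|---|---|
| One cohort, 30:15 | 1% / – / 1% | 0.07 | 0.04 | 0.04 |
| One cohort, 30:15 | 5% / – / 1% | 0.50 | 0.11 | 0.39 |
| One cohort, 30:15 | 10% / – / 1% | 0.84 | 0.13 | 0.70 |
| Parts A and B, 60:60:60 | 2% / 2% / 1% | 0.80 | 0.68 | 0.12 |
| Parts A and B, 60:60:60 | 1% / 1% / 2% | 0.69 | 0.55 | 0.14 |
| Parts A and B, 60:60:60 | 1% / 10% / 1% | 0.995 | 0.700 | 0.30 |
| Parts A and B, 60:60:60 | 0% / 10% / 1% | 0.99 | 0.45 | 0.54 |

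Gaps are taken before rounding. With three groups, the second probability is that of at least one event in at least two groups. The single-cohort rows use the low-dose cohort; a high-dose cohort has the same sizes. The gap runs from 0.04 to 0.70 with the assumed rates, so no single figure summarises it.

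**3. Causality terms.** Rules 1, 5, 6 and 7 all require that no plausible alternative explanation exists. Section 8.2.4 makes the same exclusion for its upper level. An event with a reasonable alternative explanation fails both tests. An event without one, on a plausible time course, meets both. The number of named grades differs, but I found no event that the two wordings would sort differently. In Sections 5.5 and 5.6 the terms sit in permissive lists, so a mismatch there compels nothing.

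**The case for a change.** The strongest point on the other side is that a mandatory suspension trigger should have one reading, and the text does not state it outright. The rule 6 note can also be turned round: a purely pooled count would need no unblinded help, so the note suggests that group membership matters to that wording. The iSRC charter and the Medical Monitoring Plan may define the count, but they are not among the documents. The current text still carries optional Part C and does not say that every second dose has been given, so the rules are not wholly spent.

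This stands as an observation about wording. It does not show a rule that fails when followed. The same note, by leaving rule 7 out, supports a count there that a blinded monitor can make. Other protections work separately: rules 1 to 5, the Day 8 committee reviews, the individual criterion for a single related Grade 3 event in Section 5.5, and the check before the second dose in Section 5.4. The Amendment 8 rationale says enrollment has ceased, and Part C would need the regulator's concurrence first.

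**Conclusion.** No change to the plan is called for. The text favours a pooled count under rule 7, so two subjects in one group already count when the rule is followed as written. The difference from rule 6 is then surplus language in rule 6. The causality terms are a clerical inconsistency with no demonstrated effect on any halting decision. No analysis result depends on either point, since Section 9 plans no significance testing.

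The conclusion rests on two things: the inference from the blinded monitor's role and the rule-6-only note, and the charter and monitoring plan not saying otherwise. If they did require different groups, the loss of sensitivity in a single cohort could be large, as the table shows under its assumed rates. The passages on counting and on causality should be reconciled as an editorial matter whenever the text is next touched; I take no view on which rule or scale is right.
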